### **8.2 Demographic and Screening Assessments**

Demographic data will be collected at the first study visit, and a physical examination will be conducted by a licensed physician.

A targeted medical history will be collected for all patients enrolled in the study. It includes any history of or current manifestation of signs and symptoms commonly associated with endocrine pathologies.

### **8.3 Efficacy Assessments**

Not applicable.

#### **8.4 Safety Assessments**

Any SAEs associated with study procedures will be recorded and reported.

## **9 ADVERSE EVENT REPORTING**

### **9.1 Adverse Event**

For the purpose of this protocol, the following definitions and reporting requirements will apply:

An adverse event (AE) is any untoward medical occurrence associated with the performance of a study procedure in a clinical investigation patient.

AEs may include:

- Symptoms described by the patient
- Clinically significant changes in the patient's physical exam or other signs observed by the Investigator or medical staff

Definition of a Procedure-related AE:

A procedure-related AE is an AE occurring during a clinical study that is considered by the Investigator or the Medical Monitor (or designee) to be related to a research procedure (i.e., related to the fact that a patient is undergoing a procedure in the study). For example, a procedure-related AE may be an event related to a medical procedure required by the protocol (a single blood draw or an injury from an Aerobic-surge performed in the normal course of this study).

Only serious procedure-related adverse events will be recorded.

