## **3.1 Summary of Potential Risks**

This is a randomized, cross-over study that will not include and invasive treatments methods or pharmaceutical products. The risks in this study are as follows:

- Drawing blood for diagnostic testing by venipuncture is an invasive procedure that may occasionally be associated with adverse events such as pain, bleeding, syncope, or ecchymosis.
- The Aerobic-surge, 2-minute exercise bouts will have potential risks for injuries such as falls, scrapes, bruises, pulled connective tissue injuries, etc. However this risk is no greater than the risk in daily ambulation and activity.

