#### **5.1.2 Safety Endpoints**

Only serious adverse events (SAEs) associated with study procedures will be recorded.

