### **9.3 Evaluation of Adverse Events/Serious Adverse Events**

SAEs will be assessed by the PI. Only SAEs determined by the Investigator to be possibly related or related to study procedures will be recorded. Any study-procedure-related or possibly-related SAEs ongoing after the Screening/Baseline visit will be followed until resolution.

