### **11.8.3 Adverse Events**

Only SAEs related or possibly related to invasive study procedures will be recorded.

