#### **12.4.5 Study or Site Termination**

If the NIH or its designee, the Investigator, or regulatory authorities discover any conditions during the study that indicate that the study or study site should be terminated, this action may be taken after appropriate consultation between the Sponsor or its designee and the Investigator. The Sponsor or its designee has the right to terminate the participation of either an individual site or the study at any time, for any reason which may include the following:

- The incidence and severity of AEs in this or other studies indicates a potential health hazard to patients.
- Patient enrollment is unsatisfactory.
- Data recording is inaccurate or incomplete.
- Investigator(s) do(es) not adhere to the protocol or applicable regulatory guidelines in conducting this study.

- Submission of knowingly false information from the study site to the Sponsor or its designee, or regulatory authorities.

In the event that the study is terminated early, the Sponsor or its designee will provide specific guidance to investigational sites regarding the end-of-study procedures.

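### Recording is limited to serious procedure-related events, and in 11.8.3 to invasive procedures, so most harms the protocol names would go unrecorded

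*Protocol*

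**What the plan says.** Section 9.1 defines an adverse event broadly: "An adverse event (AE) is any untoward medical occurrence associated with the performance of a study procedure in a clinical investigation patient". It counts symptoms that the patient describes, and it gives an injury during Aerobic-surge exercise as an example of a procedure-related event. The section then ends with the restriction "Only serious procedure-related adverse events will be recorded".

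Other sections repeat or vary this restriction:

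- 5.1.2: "Only serious adverse events (SAEs) associated with study procedures will be recorded".
- 9.3: "Only SAEs determined by the Investigator to be possibly related or related to study procedures will be recorded".
- 8.4 and 11.8 provide for procedure-related SAEs to be recorded, reported and listed. Neither contains the word *only*, but neither mentions non-serious events.
- 11.8.3: "Only SAEs related or possibly related to invasive study procedures will be recorded".

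Section 3.1 (Summary of Potential Risks) describes the harms that the sponsor expects. The blood draw "may occasionally be associated with adverse events such as pain, bleeding, syncope, or ecchymosis". The exercise bouts carry "potential risks for injuries such as falls, scrapes, bruises, pulled connective tissue injuries". The same section judges the exercise risk to be no higher than that of everyday activity.

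Section 12.4.5 gives examples of reasons for ending the study or closing a site. The first is: "The incidence and severity of AEs in this or other studies indicates a potential health hazard to patients".

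**The concern.** The protocol names the harms it expects, defines them as adverse events, and then tells the site not to write them down unless they are serious. This is an instruction about data collection. No analysis plan can repair it, because events that were never recorded cannot be analysed later.

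Three things are at stake:

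- **Tolerability.** The study calls itself a pilot, and whether subjects can tolerate five exercise bouts a day for 90 days is basic information for a pilot to supply.
- **The group comparison.** Subjects choose whether to add PAN-5 (7.2) and there is no randomization (7.3). If a minor injury makes someone stop exercising, that reason matters for reading the comparison, and the plan has no place for it.
- **Consistency.** Section 12.4.5 refers to AE incidence and severity, which the plan does not collect beyond related SAEs. Section 11.8.3 conflicts with the other sections on which procedures count.

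**Working it through.** The protocol states no AE rate, SAE rate or stopping threshold, so there is no figure to reproduce. The check is a cross-reading, followed by one illustration on assumed rates.

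**1. Which procedures count?** The Synopsis (Safety) treats the blood draw, the dietary changes and the exercise sessions as study procedures. Section 9.1 uses an exercise injury as an example. Sections 5.1.2, 9.3 and 11.8 refer to study procedures without qualification. Section 11.8.3 restricts recording to invasive ones, and 3.1 describes only the venipuncture as invasive. A serious fall during an exercise bout is therefore recorded under 5.1.2, 9.1 and 9.3 and listed under 11.8, but is not recorded under 11.8.3. These statements cannot all hold.

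**2. Do the named harms reach the 9.2 threshold?** The criteria in 9.2 are death, threat to life, hospitalization, disability, birth defect, and medically important events by judgment.

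- Pain, ecchymosis, scrapes, bruises and pulled connective tissue would not ordinarily meet any of them.
- Syncope, bleeding and falls usually would not, but can.

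This sorting is mine. Section 3.1 does not label its risks by seriousness, and its list of exercise injuries is open-ended.

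**3. What happens to a non-serious related event?** It is not recorded (5.1.2, 9.1, 9.3). It is not graded, because 9.3.2 grades only SAEs. It is given no outcome, because 9.3.3 covers only SAEs. It is not listed (11.8).

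**4. What does 12.4.5 have to work with?** From this trial, it has the related SAEs with their severity. It has no incidence of AEs overall and no severity for non-serious ones.

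**5. Illustration.** The inputs are n = 18 (Synopsis) and n = 20 (11.2), an assumed probability p that a patient has at least one recordable event, and independent patients. The chance of an empty record is (1 − p)^n. The chance of at least one entry is 1 − (1 − p)^n.

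| What is recorded | Assumed p | n = 18 | n = 20 |
|---|---|---|---|
| Related SAEs only: chance of an empty record | 0.1% | 0.999^18 = 98.2% | 0.999^20 = 98.0% |
| Related SAEs only: chance of an empty record | 2% | 0.98^18 = 69.5% | 0.98^20 = 66.8% |
| All related AEs: chance of at least one entry | 5% | 1 − 0.95^18 = 60.3% | 1 − 0.95^20 = 64.2% |
| All related AEs: chance of at least one entry | 20% | 1 − 0.80^18 = 98.2% | 1 − 0.80^20 = 98.8% |

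On these assumptions the present rule most likely yields an empty listing. The wider rule more likely than not yields something to read.

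**The case against.** The strongest reply is that SAE-only recording is a deliberate choice. It is stated several times and rests on the sponsor's view in 3.1 that the exercise risk is no greater than that of daily activity. For a small, non-drug pilot, wanting more data does not show an error. That is fair as far as it goes. But the rule prevents the study from checking the very view it rests on, and the contradiction in 11.8.3 is not a matter of preference.

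Several stronger readings are tempting, and the protocol does not support them:

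- *The termination ground has no data.* It has some. Related SAEs are recorded, graded and listed, and the sentence in 12.4.5 also draws on other studies.
- *A stopping rule cannot operate.* Section 12.4.5 is a discretionary right with example grounds and no threshold, so nothing is triggered by a count. Rewording that ground in terms of SAEs would remove the mismatch, though it would leave the named harms unrecorded.
- *Any muscle injury vanishes.* A torn muscle could meet the disability or medical-judgment criterion in 9.2. An ordinary strain is the safer example.
- *Subjects who stop exercising become invisible.* Compliance is tracked (7.4), so stopping would show. What would be lost is the reason.
- *The Mild and Moderate grades are useless.* Section 9.3.2 separates severity from seriousness, so an SAE may receive a lower grade.
- *The number of exercise bouts, or the upper confidence limit after zero events, measures the harm done by the rule.* The first is exposure and the second reflects the small sample. Zero related SAEs would still be informative about SAEs.

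**Conclusion.** The point holds in a limited form. Followed exactly, the plan leaves most of the harms it names unrecorded, ungraded and unlisted, and it gives 12.4.5 only related-SAE data from this trial. Section 11.8.3 also contradicts 9.1, 9.3 and 11.8 on whether a serious exercise injury is recorded at all.

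The size can only be illustrated, since the protocol offers no rates: the 66.8% to 98.2% chance of an empty record depends on the assumed SAE probability of 0.1% to 2% per patient. A reader might infer that the study would be reported as free of adverse events. The protocol plans only a listing of related SAEs and makes no such claim. This is a worthwhile, inexpensive improvement to safety information. It does not affect the validity of the weight and body-composition analysis as such.

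**What to change.** - In 5.1.2, 8.4, 9.1, 9.3, 11.8 and 11.8.3, provide for recording every AE judged related or possibly related to any study procedure (blood draw, dietary change, exercise), serious or not, with its date and 9.3.2 grade. Extend the grading in 9.3.2 to match.
- List these events by group.
- Collect them with one fixed question in the existing staff contact. The contact schedule has to be reconciled first. Section 5.2.1.1 has daily texts for 30 days and weekly contact to three months. Section 7.4 has daily tracking for 90 days. Sections 11.5 and 11.6 have daily texts for two months and weekly contact to six months.
- Keep the 24-hour IRB reporting for SAEs only.
- Reconcile the reference to invasive procedures in 11.8.3 with 9.1, 9.3 and 11.8.

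The cost is protocol wording, settling the contact schedule, a short AE log for at most 20 subjects, and a safety table that looks less clean.

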### **9.2 Serious Adverse Event**

A serious adverse event (SAE) is an AE that results in any of the following:

- Death: The patient died as the result of the event.
- Is life-threatening: An AE that places the patient, in the view of the Investigator or clinician, at immediate risk of death from the AE as it occurred, i.e., does not include an AE that had it occurred in a more severe form, might have caused death.
- Requires in-patient hospitalization or prolongation of an existing hospitalization
- Persistent or significant disability/incapacity: An AE that results in a substantial disruption of a person's ability to conduct normal life functions.
- Congenital anomaly/birth defect: A congenital anomaly/birth defect that occurs in the offspring of a patient exposed to the study procedure.

- Other Medically Important Serious Medical events: An AE that may not result in death, be life-threatening, or require hospitalization may be considered an SAE when, based upon appropriate medical judgment, the event may jeopardize the patient or patient may require medical or surgical intervention to prevent one of the outcomes listed above.

### **9.3 Evaluation of Adverse Events/Serious Adverse Events**

SAEs will be assessed by the PI. Only SAEs determined by the Investigator to be possibly related or related to study procedures will be recorded. Any study-procedure-related or possibly-related SAEs ongoing after the Screening/Baseline visit will be followed until resolution.

#### **9.3.1 Causality Assessment**

For each SAE the Investigator must determine whether, based on available evidence, there is a reasonable possibility that the study procedure caused the event. Causal relationship will be classified according to the following criteria:

- Not Related: There is no suspicion of a causal relationship between the procedure and the AE.
- Unlikely Related: There is no evidence for a causal relationship between the procedure and the AE; however, such a relationship cannot be ruled out.
- Possibly Related: There is some evidence supporting the possibility of a causal relationship between the procedure and the AE.
- Related: There is strong evidence that there is a causal relationship between the procedure and the AE.

A causality assessment must be provided for each SAE recorded even if there is only limited information at the time.

Upon receipt of follow-up information, the Investigator may change his/her assessment of causality and amend the SAE report accordingly.

#### **9.3.2 Severity**

Severity indicates the intensity of the event and should not be confused with seriousness (i.e., Section 9.2), which is an event outcome applied for the purpose of event classification and regulatory reporting.

#### **Severity Grading**

The Investigator will assess the severity of all study-procedure-related SAEs as Mild, Moderate, or Severe, based on the following definitions.

## **Definitions:**

- Mild: A type of AE that is usually transient and may require only minimal treatment or therapeutic intervention. The event does not generally interfere with usual activities of daily living.
- Moderate: A type of AE that is usually alleviated with additional specific therapeutic intervention. The event interferes with usual activities of daily living, causing discomfort, but poses no significant or permanent risk of harm to the research participant.
- Severe: A type of AE that interrupts usual activities of daily living, or significantly affects clinical status, or may require intensive therapeutic intervention.

### **9.3.3 Outcome**

Outcome describes the status of the SAE.

The Investigator will provide information regarding the patient outcome of each SAE that is judged to be possibly related or related to a study procedure.

**Definitions** for possible results of an AE outcome:

- Recovered/Resolved: the event has improved or recuperated
- Recovering/Resolving: the event is improving
- Not Recovered/Not Resolved: the event has not improved or recuperated
- Recovered/Resolved with sequelae: the patient recuperated but retained pathological conditions resulting from the prior disease or injury
- Fatal: termination of life as a result of an adverse event; there should be only one AE marked with this outcome
- Unknown: not known, not observed, not recorded or refused

### **9.3.4 Action Taken Regarding the Investigational Product**

Not applicable.

## 9.4 Reporting Serious Study-Procedure-Related Adverse Events

### 9.4.1 Initial Reporting of Serious Study-Procedure-Related Adverse Events

Study-procedure-related or possibly related SAEs should be recorded using appropriate medical terminology. When recording, it is preferable to provide a diagnosis. In the absence of a diagnosis, each sign and symptom should be captured as a unique SAE. Sufficient information should be sought to assist the Investigator both in determining the diagnosis and in making a causality assessment.

The necessity and time requirements for reporting of study-procedure-related or possibly related SAEs to the Sponsor or its designee and/or regulatory agencies are as follows:

- All SAEs related or possibly related to study procedures must be reported to the IRB or designee within 24 hours of the Investigator's first knowledge of the event.
- A completed Clinical Study SAE Report Form containing a detailed written description of the event along with available supporting documents (e.g., discharge summary, autopsy report, diagnostic test results, etc.) should be provided by fax or e-mail to the following address:

Safety Reporting [name], BSN, CPN
[contact] E-mail: [contact]

- Additional information that is not available at the time the initial SAE Report Form was completed, must be promptly reviewed and provided to the IRB within 48 hours of receipt. Full supporting documentation should be solicited by the investigative site even if the SAE occurred at another institution. Such documentation may include copies of relevant patient/hospital records, discharge summaries, laboratory/test results or autopsy reports.
- If, at any time after the patient has completed participation in the study (as defined in Section 0), the Investigator or study staff becomes aware of an SAE that they suspect is related to the study procedures (see Section 9.3.1), then the event and any known details must be reported promptly to the Sponsor or its designee, following the reporting instructions in Section 9.4.3.

#### **9.4.2 Follow-Up of Serious Adverse Events**

**All SAEs related or possibly related to study procedures** will be followed until resolution, the condition stabilizes, or the Investigator and Sponsor agree that follow up is no longer necessary.

Rules for SAE follow up apply to all patients, to the extent allowed by the patient's consent. The Investigator will ensure that follow up includes further investigations consistent with appropriate medical management to understand the nature and/or causality of the SAE. The Sponsor/designee, or regulatory authorities may also request additional information regarding an SAE at any time.

All follow-up information must be promptly reviewed by the Investigator and provided to the Sponsor within the specified timelines. Additional procedure-related SAEs may be identified during the review of follow-up information and should be processed in accordance with requirements defined throughout Section 10.

#### **9.4.3 Reporting to Regulatory Authorities, Investigators and IRB**

The Sponsor will ensure that processes are in place for provision of study-procedure-related or possibly related SAE reports to Investigators and institutional review boards (IRBs) or institutional ethics committees as required, within the specified timelines.

The NIH or its designee will submit study procedure-related or possibly related SAE reports to the Investigator as required. In the US, Investigators will report study procedure-related or possibly related SAEs to their IRB in accordance with applicable standard operating procedures and/or local reporting requirements.

Investigators must forward copies of the IRB notification to the Sponsor or its designee, when applicable.

#### **9.5 Pregnancy Reporting**

Pregnancy will be reported to the PI immediately upon receipt of this test by the subject.

## **10 DATA COLLECTION, QUALITY ASSURANCE, AND MANAGEMENT**

### **10.1 Recording of Data**

Copies of pertinent records in connection with the study, including all source documents, will be made available to the NIH, IRB, or its designee on request with due precaution towards protecting the privacy of the patient.

The PI may elect to have data entered by the clinical site directly into an electronic system using electronic case report forms, eCRFs.

Data will be entered by the site into the eCRFs in the electronic data capture (EDC) system that is 21 Part 11 compliant. Unless explicitly directed, blank data fields are not acceptable. Any erroneous entries made in the eCRFs must be corrected. Changes made to the data after initial entry into the eCRF will be captured via an electronic audit trail, and include the reason for change. Incomplete entries or entries needing additional explanation will be highlighted or queried to the Investigator for clarification.

Adverse events may be coded with the latest version of the medical dictionary for regulatory activities (MedDRA) available at study initiation. Similarly, prior and concomitant medications and concomitant therapies may be coded using the latest version of World Health Organization (WHO) drug available at study initiation. If used, the versions employed at study start will be maintained throughout the project.

### **10.2 Data Quality Assurance**

Study monitors will perform source document verification according to the clinical monitoring plan to ensure there are no inconsistencies between the eCRFs and source documents. Discrepancies will be resolved in accordance with the principles of Good Clinical Practice.

### **10.3 Data Management**

Data management will be coordinated by Galveston Clinical Research or its designated representative in accordance with the study data management plan.

## **11 STATISTICAL METHODS AND PLANNED ANALYSES**

### **11.1 General Considerations**

The dependent variables will include change in Body Composition (weight, Fat%), and BMI.

Independent variables will include age, gender, ethnicity, and duration of obesity.

### **11.2 Determination of Sample Size**

This is a pilot study and will recruit 20 potential subjects.

### **11.3 Analysis Sets**

All study patients for whom data are available will be included in the analysis dataset. All study patients who complete the 30-day assessments will be included in the safety dataset.

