# 1 SYNOPSIS

**TITLE: Food Allergen Elimination and a Brief, Therapeutic Exercise for Obesity Reduction**

**OBJECTIVES:**

Primary: The purpose of this study was to determine if removing food allergens alone or combined with a multi-discipline weight loss protocols are effective in obesity reduction.

NAME OF COMPANY: Galveston Clinical Research Foundation

STUDY SITES: Galveston, Texas, USA

METHODOLOGY: Randomized, Controlled, Cross-over Trial

NUMBER of PATIENTS: 18

Inclusion:

- 1) Healthy adults, ages 20 – 75
- 2) Body Mass Index  $\geq 30$

Exclusion:

- 1) Cardiovascular Heart Disease
- 2) Hypothyroid Secretion (Can reapply after Treatment and normal TSH, T3, T4 levels)
- 3) Hypogonadal syndrome (Can reapply after Treatment and normal testosterone levels.)
- 4) CVA, TBI or any neural injury or disease
- 5) Diabetes Mellitus (Type I or II)
- 6) Other weight loss protocols, diets, or medication (30 day wash out)

Randomized Categorization

- N/A

STATISTICAL METHODS:

A Repeated Measures ANOVA will measure changes in weight, body composition, and BMI.

SAFETY:

Serious Adverse Events associated with study procedures (ALCAT Blood draw, dietary changes and 2-minute exercise sessions) will be reported to the IRB within 24 hours and to the FDA as required by IRB.

**2.**

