#### **5.2.1 Completion of a Subject's Participation and the Overall Study Completion**

Each subject's will be followed through completion of the 90-day trial.

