##### **5.2.1.2 Premature Patient Discontinuation from the Study**

Patients are free to withdraw consent and/or discontinue participation in the study at any time, without prejudice to further treatment. A patient's participation in the study may also be discontinued at any time at the discretion of the Principle Investigator or Primary Care Physician.

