### **11.8.6 Missing or Invalid Data**

N/A

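### With missing data marked N/A and only patients with data analysed, the planned ANOVA is in effect a completers analysis that may bias the weight change

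*Protocol*

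**What the plan says.** Four parts of the protocol bear on this point.

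- **Analysis set (section 11.3).** "All study patients for whom data are available will be included in the analysis dataset". No set of all enrolled subjects is defined. The safety set is narrower: "All study patients who complete the 30-day assessments will be included in the safety dataset". Section 11.4 builds the demographic and baseline tables on that safety set.
- **Missing data (section 11.8.6).** Under the heading "Missing or Invalid Data" the entire entry is N/A.
- **Method and outcome.** The Synopsis says: "A Repeated Measures ANOVA will measure changes in weight, body composition, and BMI". Section 11.1 defines the outcomes as changes: "The dependent variables will include change in Body Composition (weight, Fat%), and BMI".
- **Withdrawal and follow-up.** Section 5.2.1.2 says: "Patients are free to withdraw consent and/or discontinue participation in the study at any time, without prejudice to further treatment". It also lets the investigator or the primary care physician end participation. Section 5.2.1 states the intention: "Each subject's will be followed through completion of the 90-day trial". Sections 5.2.1.1 and 7.4 provide for text or weekly contact during the 90 days.

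The protocol gives no expected dropout rate and does not say that weights are collected after a subject stops the programme.

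**The concern.** The protocol foresees withdrawal and yet enters missing data as not applicable. A subject who leaves before any follow-up weighing has no change value, and a conventional repeated measures ANOVA drops any subject with an incomplete set of measurements. The reported mean change would then describe those who stayed, not those who started.

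That matters if staying is related to the result. In a weight-loss programme it is plausible that people who see little benefit leave sooner, and the mean loss among completers would then look better than the mean loss among all who began. The comparison of allergen elimination alone with the combined programme could also be distorted if dropout differs between the two groups.

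Because the baseline tables use only those who complete the 30-day assessments, early leavers would be absent there too. A reader could not see who had been lost.

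**Working it through.** **Step 1: does the plan amount to a completers analysis?** Section 11.3 alone does not say so, since its wording could admit subjects with partial data. The restriction arises when it is combined with an outcome defined as change (11.1), a repeated measures ANOVA (Synopsis) and no rule for incomplete subjects (11.8.6). A subject with only a baseline weight cannot contribute a change. Section 8.1 lists only the initial body composition test, so the number of later weighings is not fixed. If there is only one, at day 90, everyone without it is lost.

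**Step 2: is there a stated figure to reproduce?** No. The protocol gives 18 subjects (Synopsis) or 20 (section 11.2), with no effect size, SD, power or dropout rate. At 20% to 30% dropout, 14.4 to 12.6 of 18 or 16 to 14 of 20 would remain.

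**Step 3: bias by simple arithmetic.** Let *d* be the dropout proportion. Then

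all-enrolled mean = (1 − *d*) × completer mean + *d* × leaver mean,

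so completer mean − all-enrolled mean = *d* × (completer mean − leaver mean).

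Take an assumed completer mean of −5 kg, the size of the change in the food-elimination study cited in the Introduction. The last four columns show by how much completers overstate the loss:

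| Leavers' mean change (assumed) | 10% | 20% | 30% | 40% |
|---|---|---|---|---|
| 0 kg | 0.5 kg | 1.0 kg | 1.5 kg | 2.0 kg |
| −2.5 kg | 0.25 | 0.5 | 0.75 | 1.0 |
| −5 kg | 0 | 0 | 0 | 0 |
| −7.5 kg | −0.25 | −0.5 | −0.75 | −1.0 |

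Example: at 20% dropout with leavers at 0 kg, 0.8 × (−5) + 0.2 × 0 = −4.0 kg, against −5 kg in completers.

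**Step 4: bias under a dropout model.** Assume normally distributed changes and logit(probability of dropout) = *a* + *b* × (worse change in SD units), with *a* solved to give each dropout rate. A slope *b* = 1 means the odds rise by e¹ = 2.7 per SD.

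| Dropout | Bias, *b* = 1 (SD) | With assumed SD of 5 kg |
|---|---|---|
| 10% | 0.09 | 0.5 kg |
| 20% | 0.17 | 0.9 kg |
| 30% | 0.25 | 1.3 kg |
| 40% | 0.33 | 1.7 kg |

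(The kg column is computed before rounding the SD column.) Slopes of 0.5 to 1.5 give 0.10 to 0.23 SD at 20% dropout and 0.14 to 0.33 SD at 30%. At *b* = 0 the bias is zero. At *b* = −1 it has the same size with the opposite sign.

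**Step 5: the group contrast.** With *b* = 1 in both groups and dropout of 10% in one and 30% in the other, the contrast is biased by 0.25 − 0.09 = 0.16 SD, or 0.8 kg, in favour of the group with more dropout. A second illustration assumes completer means of −5 kg (allergen elimination alone) and −8 kg (combined), with leavers at 0 kg. The completers' contrast is −3.0 kg. The all-enrolled contrast is:

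- dropout 10% alone, 30% combined: 0.7 × (−8) − 0.9 × (−5) = −5.6 + 4.5 = −1.1 kg;
- dropout 30% alone, 10% combined: 0.9 × (−8) − 0.7 × (−5) = −7.2 + 3.5 = −3.7 kg.

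So completers may overstate or understate the difference.

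**The case against.** **The direction is assumed.** A reader might infer that the plan will overstate weight loss. The documents do not support that as a certainty: they give no dropout rate, no SD and nothing on how leavers fare. This objection stands.

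**Heavier dropout in the combined group is speculative.** A reader might also infer that the more demanding regimen must lose more subjects. The five daily meals and exercise bouts do belong to PAN-5, but section 7.2 has subjects volunteer for it, and volunteers may be more motivated and stay longer. This stands too.

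**Section 11.3 is inclusive and N/A may be an unfilled template field.** N/A also fills other entries, such as Other Endpoints and Interim Analysis, and details of incomplete data commonly sit in a SAP. This stands in part. The wording of 11.3 is compatible with a model that uses all available data. But the protocol is not silent here: it has a missing-data section and enters not applicable, which does not fit section 5.2.1.2.

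**Follow-up is already provided for.** Section 5.2.1 intends 90 days for each subject, and staff are in regular contact. This helps, but nothing says that a weight is sought after withdrawal.

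**The scale is modest for a pilot.** With an assumed SD of 5 kg and 10 subjects per group, the standard error of a difference is √(25/10 + 25/10) = 2.2 kg, so a bias of 0.8 kg is about a third of it. That is fair and limits the priority. It does not remove the point, since the correction is cheap.

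**A mixed model alone would not cure it.** Correct. It assumes that data are missing at random, adds little for subjects with only a baseline value, and does not remove dropout that depends on the unseen final weight.

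**Conclusion.** The point holds in limited form. Sections 11.3, 11.8.6 and 11.1 and the Synopsis, taken together, give what is in effect a completers analysis, in a trial that expressly allows withdrawal. The mean change may be biased, plausibly towards greater loss, but neither the existence nor the direction of bias can be established from the protocol.

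The illustrative size is 0.9 to 1.7 kg at 20% to 40% dropout, against a cited change of 5 kg. It rests on three assumptions that the documents do not supply: the dropout rate, the SD of 5 kg and the 2.7-fold odds per SD. The defect lies in a plan that can neither reveal nor bound the bias, whichever way it runs. It should be corrected, with priority suited to a small pilot.

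**What to change.** - **Section 11.3:** define the efficacy set as all enrolled subjects with a baseline weight, in the group in which they started.
- **Section 11.8.6:** replace N/A with three rules. (1) A day-90 weight is sought from every enrolled subject who still consents to contact, including those who stopped the programme. (2) All available weights are analysed, for example with a mixed model. (3) A sensitivity analysis sets change to zero for those still missing.
- **Reporting (sections 11.3 and 11.4):** give dropout and baseline characteristics by group for everyone enrolled, not only for those who complete the 30-day assessments.

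The first rule and the dropout report carry most of the benefit, because they bear directly on outcome-related loss. The zero-change analysis is one convention among several and can err the other way, so it serves as a check and not as the main result.

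The cost is a few sentences, slight extra follow-up through contact that already exists, and one more analysis. The reported mean loss may turn out less favourable. Sample size and treatment are unchanged.
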